This study is a sub-study of an “Ocular Surface and glaucoma. A randomized study of IOP reducing eye drops versus surgical intervention” study (REK no. 253485). Invited to participate in the study are men and women between 50 and 75 years of age with early POAG, diagnosed in agreement with the European guidelines for glaucoma diagnoses and staging of the disease, with MD loss of less than 5 dB on visual fields and with a clinically significant cataract eligible for surgery, who come for a routine glaucoma follow-up examination and a presurgical assessment for cataract extraction at the ophthalmology practice of Ifocus Øyeklinikk in Haugesund, Norway, in the period between August 2021 and February 2022.

Exclusion criteria:

- Recent changes (<3 months) in the treatment with topical IOP-lowering medications (i.e., active pharmacological substance, dosage, preservatives) based on the patient medical journals.
- Use of more than one IOP-lowering eyedrops with different active pharmacological substances based on the patient medical journals.
- Self-reported OSD comorbidity defined as an autoimmune or inflammatory disease, such as Sjogren’s syndrome or Rheumatoid Arthritis (RA), or any other systemic disease that can directly affect the ocular surface.
- Conditions that may confound the results of the study:
 - Self-reported acute or chronic diseases such as connective tissue disease, clinically significant atopic disease, diabetes type 1 and 2, immunocompromised, or any other such condition.
 - Manifest corneal disease, dystrophy, or scarring based on the clinical exam.
 - Corneal ectasia based on the clinical exam.
 - Lid deformities based on the clinical exam.

- Recent intra- or extra-ocular surgery based on the patient medical journals.
- Previous refractive procedures like LASIK, LASEK, or radial keratotomy based on the patient medical journals.
- A previous corneal transplant, DSAEK, lamellar keratoplasty, or similar procedure based on the patient medical journals.

Recruitment:

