Ocular surface staining (OSS) or superficial punctate staining is an inflammation marker presented as fine, scattered, punctate corneal epithelial loss or damage. Operationally, OSS is defined as a punctate staining pattern on the ocular surface that can be observed with slit-lamp biomicroscopy when the tear film is tinted with fluorescein sodium (MINIMS® Fluorescein Sodium 2%, Bausch&Lomb) and using a yellow filter (HUVITZ Microscope Slit-lamp HS-7000) and cobalt blue light. Evaluation of corneal staining is based on the Oxford schema (Bron, Evans, & Smith, 2003), which is used to estimate surface damage in dry eyes. Staining is subjectively assessed and graded in 0.5 steps on an ordinal scale using a clinical grading scale that ranges from 0 (absent) to 5 (severe) for the right and the left eye.

Meibum quality is defined as the degree of viscosity of the oil secreted from the Meibomian glands. Operationally, meibum quality is defined as the subjective assessment of the content of the meibomian glands by applying moderate digital pressure on each of the eight glands of the central third of the lower lid with a flat, perpendicular surface like index finger or Q-tip for 10 seconds. Properties of the expressed content of the glands are evaluated and registered in whole numbers on the ordinal scale from 0 to 3 (0=clear meibum; 1=cloudy meibum; 2=cloudy with debris (granular); 3=thick, like toothpaste) for each of the eight glands (Nichols et al., 2011) for the right and the left eye.

Meibum expressibility is defined as a combination of the viscosity and the integrity of the channels and orifices that make up for expressibility. Operationally meibum expressibility is defined as an ability to express the content of the meibomian glands in five central glands in the lower eyelid by applying moderate digital pressure on the glands. Evaluation of the meibum expressibility is performed simultaneously with an evaluation of the Meibum quality. Expressibility is recorded in whole numbers on

the ordinal scale from 0 to 3 (0=all glands expressible, 1=3-4 expressible, 2= 1-2 expressible, 3=non expressible) (Nichols et al., 2011).

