Subjects included in this study will undergo a comprehensive tear film evaluation on both eyes. All examinations will be performed by an experienced observer ([name]) in the fixed order from the least to the most invasive one. Firstly, **OSD-related disability (OSDI)** (Appendix 2), and **The nature of the symptoms (SPEED II)** (Appendix 3) will be examined by means of questionnaires. The patient will be given approximately 5 minutes to complete the questioners. The examiner will be in the room with the patient and will provide only a general explanation. The examiner will avoid interpreting or rephrasing the questions. The OSDI questioner has shown good specificity (0.83) and moderate sensitivity (0.60) when differentiating between dry eye disease patients and healthy patients (Schiffman et al., 2000). The sensitivity and specificity for the SPEED II questioner are 0.90 and 0.80 (Ngo et al., 2013). Thereafter, clinical examinations will be performed on the right eye followed by the left eye in this order: **Tear film osmolarity, Non-invasive Keratograph tear break-up time (NIK BUT), Bulbar redness, Tear Meniscus Height, Tear production (Schirmer 1 test), Ocular surface staining (OSS), Meibum quality, Meibum expressibility, Corneal sensitivity, Meibomian gland dropout.** **Tear film osmolarity** will be measured with The TearLab Osmolarity System by TearLab Corporation that has a precision (CV) of 1,5% with a standard deviation (Stdev) of 5.0 mOsm/L and accuracy of $r^2=0,95$. Tear collection will be performed at the lateral (temporal) extent of the eyelid, and the test card should touch the lower temporal tear meniscus. **Non-invasive Keratograph tear break-up time (NIK BUT), Bulbar redness, and Tear Meniscus Height (TMH)** will be measured with The Oculus Keratograph 5M by OCULUS, Inc. The patient will be instructed to place head correctly in the chinrest, and when the Keratograph is aligned with the patient's face, the patient will be instructed to blink twice. After the second blink, the measurement of the NIK BUT will automatically begin. The patient will be encouraged to keep their eyes open as long as possible without blinking. The

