measurement is automatically stopped by the device if the patient moves or blinks. **Bulbar redness** will be measured and graded automatically and objectively by taking a picture with the Oculus Keratograph 5M. Similarly, **Tear Meniscus Height (TMH)** will be measured objectively from the picture taken with Oculus Keratograph 5M that has an integrated ruler and various magnification options. Following, **Schirmer 1 test** will be performed without anesthetics. The free end of the non-toxic calibrated filter paper will be placed in the temporal part of the lower eyelid of both eyes, and the patient will be asked to hold the eyes gently closed for 5 minutes. At the end of the 5-minute interval, the paper strips will be removed from each lower eyelid, and the amount of wetting of the paper will be noted. Slit-lamp examination of the anterior segment will be performed in order to evaluate **Ocular surface staining (OSS)**. A quantified 5 µl of 2% Fluorescein sodium will be instilled into each conjunctival sac with a micro-pipette (using a sterile tip), and then observation will be done with a slit-lamp using a yellow filter and cobalt blue light. **Meibum quality** and **Meibum expressibility** will be also evaluated during the slit lamp exam. Meibum quality will be assessed in each of the eight glands of the central third of the lower lid by applying pressure on the eyelid with a Q-tip. It will be estimated and graded on a scale from 0 to 3 for each gland: 0=clear, 1= cloudy, 2= cloudy with debris (granular), and 3= thick, like toothpaste (total score range, 0–24) (Nichols et al., 2011). **Meibum expressibility** will be assessed in the five central glands in the lower lid by applying pressure on the lid with a Q-tip. It will be estimated on a scale from 0-3 (0= all glands expressible; 1=3-4 glands expressible; 2= 1-2 glands expressible; 3=no glands expressible) according to the number of glands expressible (Nichols et al., 2011). **Cochet – Bonnet Aesthesiometer** will be used to measure corneal sensitivity. Fine nylon filament, the length of which can be adjusted (60 mm to 5 mm), will be used to apply different intensities of stimuli on the corneal surface. The shortest length of the filament that the patient reacts will be noted. **Meibomian gland dropout (Meibography)** will be measured by taking infrared photos of the upper and lower eyelid with Oculus Keratograph 5M with minimal discomfort to the patient. Gland tissues will be made visible by everting the upper and lower eyelids with a Q-tip and using Meibo-Scan. The degree of Meibomian dropout will be scored and noted for all four eyelids. Finally, **Self-reported compliance** will be examined by means of simple interview question of how often one may skip a dose (Appendix 4). Information's about age, gender, duration of the treatment, the active pharmacological substance, and the preservatives in the topical IOP-lowering medication will be collected from the patient journals.

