
Analyses:

The results of the comprehensive tear film evaluation will be recorded in the patient journal system (Infodoc Plenario) used at the Ifocus Øyeklinikk, Haugesund, Norway. The data collected with the Oculus Keratograph 5M by OCULUS, Inc. will be stored in a separate database called Oculus Patient Data Management. Once measurements are performed, data related to the study will be transferred from the patient journal to a data registration form (Appendix 4). The names of the patients will be replaced with ID numbers. All data will be transferred to and organized in a database (Excel, Microsoft Inc.). To identify empty cells or unrealistic values, an algorithm in Excel will flag the cells in question. A quality-assured version of the database will constitute the basis for statistical analyses. For variables measured on a numerical scale, these summaries will include the sample size, as well as the mean, standard deviation, median, minimum, and maximum. For variables measured on a categorical scale, summaries will provide the number and percentage of subjects who provided each score. Preliminary considerations of the data will include the investigation as to whether any transformation (i.e., logarithmic) should be applied prior to the statistical analyses. For categorical data, the sparseness of the data across categories will be considered, and the combination of categories prior to statistical analysis will be applied where deemed appropriate. For variables measured on a continuous scale, the statistical significance of the difference

between groups will be investigated using an Analysis of Variance (ANOVA) with appropriate post-hoc testing. For variables measured on an ordinal categorical scale, the Kruskal-Wallis signed-rank test will be employed. Questionnaire data will be analyzed using current standards. The statistical analyses will be performed using SPSS version 24. All statistical tests of hypotheses will employ a level of significance of $\alpha=0.05$. Odds ratios with 95% confidence intervals may also be used.

Project management and organization:

Principal investigator: [name]

Project manager: [name]

Resources, equipment, and physical facilities:

All equipment is available in the ophthalmic practice Ifocus Øyeklinikk in Haugesund, Norway, where the study will take place:

- The TearLab Osmolality System by TearLab Corporations.
- The Oculus Keratograph 5M by OCULUS, Inc.

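### Nothing in the protocol keeps the drop and its preservative from the single observer who grades staining, the one subjective sign, so grading could drift towards hypothesis 1

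*Protocol*

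**What the plan says.** - **Grading.** Under Outcome variables, staining follows the Oxford schema from 0 to 5 for each eye: "Staining is subjectively assessed and graded in 0.5 steps on an ordinal scale using a clinical grading scale".
- **Observer.** Under Methods, Measurements: "All examinations will be performed by an experienced observer". No second grader is mentioned.
- **Recording.** Under Analyses: "The results of the comprehensive tear film evaluation will be recorded in the patient journal system". Transfer to the data registration form, with ID numbers in place of names, comes after the measurements.
- **Exposure.** The Measurements section closes by stating that "the active pharmacological substance, and the preservatives in the topical IOP-lowering medication will be collected from the patient journals". The exclusion criterion on recent treatment changes also rests on the journal: "active pharmacological substance, dosage, preservatives) based on the patient medical journals". Under Predictor variables, the substance is to be known from the patient history.
- **Use in the hypotheses.** Research objectives and significance defines signs of OSD by four alternatives: hyperosmolarity, reduced NIKBUT, staining or a reduced Schirmer 1 test. Hypothesis 1 expects more signs with preservatives. Hypothesis 3 expects the frequency of signs to be modified by the substance, without naming a direction.

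The protocol does not say that the observer is masked to the drop, and it does not say that the observer is unmasked.

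**The concern.** Three features meet. The sign is graded by judgement in half-steps. The grade is written into the same kind of record that holds the exposure. The main hypothesis has a stated direction, and the introduction already treats preservative toxicity as established. An observer who knows which drop a patient uses may resolve doubtful half-steps in the expected direction without intending to.

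Because the four signs are joined by "or" in the definition's logic, staining alone can make a patient positive. Osmolarity and NIKBUT are instrument readings and Schirmer wetting is read in millimetres, so the exposure to grader expectation falls mainly on staining. The protocol also gives no staining grade at which the sign counts as present. That is a separate gap, but it leaves more room for a half-step to matter.

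This belongs in the protocol. Who grades, what that person can see and the order of recording are rules of conduct, and no later analysis can separate a grader's expectation from a preservative effect.

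**Working it through.** The protocol gives no figure to reproduce here. The target of 30 subjects is justified by feasibility, without an event rate or effect size.

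**Step 1: can the exposure reach the grader?** Four statements bear on it.
- Eligibility needs substance, dosage and preservative to be read from the journal. The protocol does not say who does this.
- All examinations fall to one observer.
- Findings are recorded in the journal system first and coded afterwards, so ID numbers protect privacy but do not mask grading.
- Extraction of substance and preservative is listed last in Measurements, after the examinations. This points the other way, but it is an order of description and not a rule that grades are locked first.

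Taken together, knowledge of the drop at grading is likely and nothing prevents it. It is not stated.

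**Step 2: how large could the effect be on staining alone?** Every input is assumed. True staining frequency is p = 0.30 in both groups, and a fraction m = 0.10 to 0.20 of unstained preservative users is graded up to positive.
- False difference = (1 − p) × m
- m = 0.10: 0.70 × 0.10 = 0.07, or 7 points
- m = 0.20: 0.70 × 0.20 = 0.14, or 14 points

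The introduction quotes 22% to 78% for OSD as a whole, depending on the test. Using that as a range for p with m = 0.20:
- p = 0.22: 0.78 × 0.20 = 15.6 points
- p = 0.50: 0.50 × 0.20 = 10.0 points
- p = 0.78: 0.22 × 0.20 = 4.4 points

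**Step 3: how large on the four-sign composite?** Let r be the share of patients already positive on another sign, assumed independent of staining. An upgrade matters only in the remainder:
- False difference = (1 − r) × (1 − p) × m, with p = 0.30

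| r | m = 0.10 | m = 0.20 |
|---|---|---|
| 0.30 | 0.70 × 0.07 = 4.9 points | 0.70 × 0.14 = 9.8 points |
| 0.50 | 0.50 × 0.07 = 3.5 points | 0.50 × 0.14 = 7.0 points |
| 0.70 | 0.30 × 0.07 = 2.1 points | 0.30 × 0.14 = 4.2 points |

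**Step 4: what would this do to a test?** Exact enumeration of two binomials, assuming a subject-level comparison of 15 with 15, no true difference and two-sided alpha 0.05. The columns give the chance of rejection.

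| Outcome (p = 0.30) | m | Uncorrected chi-square | Fisher exact |
|---|---|---|---|
| Staining alone | 0 | 5.5% | 1.7% |
| Staining alone | 0.10 | 7.2% | 2.5% |
| Staining alone | 0.20 | 12.4% | 5.2% |
| Composite, r = 0.30 | 0 | 4.6% | 1.7% |
| Composite, r = 0.30 | 0.20 | 7.9% | 3.3% |
| Composite, r = 0.70 | 0 | 5.1% | 1.7% |
| Composite, r = 0.70 | 0.20 | 5.7% | 2.1% |

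Under these assumptions the effect on false positives is moderate for staining reported alone and small for the composite.

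**The case against.** The strongest reply is that the observer's knowledge is inferred. No section says that medication data are in view during grading. Exposure extraction is described after all the examinations, nobody is named for the eligibility check, and the remark that the substance is known from the history does not mention the preservative, which is the exposure in hypothesis 1. This stands: a reader might infer that the protocol describes an unmasked grader working with the drop in front of them, and the text does not support that. What remains is that nothing prevents it.

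Second, grading is anchored by the Oxford schema, a yellow filter with cobalt blue light, a measured fluorescein volume and a fixed test order. These limit drift between examinations, but they do not mask the observer.

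Third, the 7-14 points describe staining alone, the upgrade rate has no source in the protocol, and moving a patient to positive presumes a cut-off that the protocol does not give. All of this stands. A reader might conclude that any positive result on OSD signs could be put down to the grader. With the composite shift at about 2-10 points, that goes too far.

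Fourth, one might widen the point to meibum quality, meibum expressibility and gland dropout, or carry the directional argument over to hypothesis 3. The three lid measures appear in no hypothesis, and hypothesis 3 states no direction, so neither extension is supported to the same degree.

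**Conclusion.** The point holds as a gap in the design that is cheap to close. One observer grades the only subjective component of the signs definition, the record flow runs journal first and coded form second, and no rule keeps the exposure from that observer. Bias towards hypothesis 1 is possible and cannot be removed afterwards, but the protocol does not show that it occurs and its size cannot be computed from the document.

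The illustrated size is 7-14 points for staining alone and about 2-10 points for the composite. It rests on 30% true staining in both groups, upgrading of 10-20% of unstained preservative users only, 30-70% already positive on another sign, and independence between the signs. It is a should-fix improvement with medium confidence. A sentence stating that the observer is already masked in practice, and how, would resolve it.

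**What to change.** In Methods (Measurements) and Analyses, set the order of recording:

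1. The observer enters staining and the other slit-lamp grades on an ID-coded sheet with no medication fields, before the medication record is opened for that visit. The appendix form is not shown. If it holds the predictor fields as well, a separate sheet is needed.
2. The grades are locked and then copied to the journal.
3. Substance, preservative and duration are extracted only after that.
4. Patients are asked not to mention their drops during the examination.
5. Where existing staff allow, someone other than the observer does the journal eligibility check. Whether the named project roles permit this cannot be told from the text. If they do not, report the observer as not fully masked and name it as a limitation.

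Grading the stored meibography images in one batch by ID is a useful extra, but it concerns a measure outside the hypotheses and does nothing for staining, which is observed live at the slit lamp.

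The cost is a small reordering of paperwork, with no added visit or patient procedure. Masking stays incomplete if the observer already knows the patient or the patient names the drop.

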Signs and symptoms of OSD are often non-specific to the ocular surface and caused by allergic, pro-inflammatory, or toxic conditions (Stewart et al., 2011). Ocular surface toxicity, especially to benzalkonium chloride (BAK) preservative, has been established and thoroughly discussed in the literature, which is why preservative-free treatment options are increasingly advocated, especially in patients already presenting with OSD (Stewart et al., 2011; Zhang et al., 2019). Performing a comprehensive tear film assessment in glaucoma patients may be beneficial and lead to a better understanding of the disease. To the best of our knowledge, no studies performed a full ocular surface assessment in glaucoma patients on topical treatment with IOP-lowering eye drops.

Research objectives and significance:

The main objective of the study is to investigate signs and symptoms of ocular surface disease in patients on topical glaucoma medications.

The main objective of the study is based on the following research questions:

1. What is the occurrence of signs and symptoms of ocular surface disease (OSD) in patients with primary open-angle glaucoma (POAG) who have been on treatment with IOP-lowering eye drops for at least three months?
2. Is the occurrence of signs and symptoms of OSD in patients with POAG related to added preservatives in the IOP-lowering eye drops?
3. Is the occurrence of signs and symptoms of OSD in patients with POAG modified by the active pharmacological substance in the IOP-lowering eye drops?

4. Is the occurrence of signs and symptoms of OSD in patients with POAG related to the duration of the treatment with the IOP-lowering eye drops?

Based on research questions 2-4, the following hypotheses were formulated:

1. In a sample of patients with POAG, who have been on treatment with IOP lowering eye drops for at least three months, the frequency of signs of OSD, defined as hyperosmolarity, reduced NIKBUT, ocular surface staining, or reduced Schirmer 1 test, is greater in patients that are on eye drops with preservatives compared with those that are not.
2. In a sample of patients with POAG, who have been on treatment with IOP lowering eye drops for at least three months, the frequency of symptoms of OSD, defined as OSDI index ≥ 13 or SPEED II values >5 , is greater in patients that are on eye drops with preservatives compared with those that are not.

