Corneal sensitivity is defined as the ability of the cornea to sense a variety of stimuli. Operationally, it is defined as the threshold for corneal surface to sense the touch of a fine nylon filament (0,12 mm) applied to the corneal apex by means of a Cochet-Bonnet Aesthesiometer (Luneau Technology Group). The length of the nylon filament can be adjusted (from 60 mm (highest sensitivity) to 5 mm (lowest sensitivity)). It is measured in millimeters and registered with one decimal on a numerical scale for the right and the left eye.

Meibomian gland dropout is defined as partial or total loss of acinar tissue of the meibomian glands and its function in the upper and lower eyelid. Operationally, meibomian gland dropout is defined as changes in the morphological appearance in the meibomian glands of the upper and the lower eyelid evaluated by means of infrared trans-illumination of the lids using an Oculus Keratograph 5M (OCULUS, Inc). Gland tissues are made visible using Meibo-Scan software and classified on the Meiboscale grading scale from a photograph taken with Oculus Keratograph 5M (Pult & Riede-Pult, 2013). It is registered in whole numbers on an ordinal scale that ranges from 0 to 4 (0=0% loss; 1= \leq 25%; 2=26%-50%; 3=51%-75%; 4= \rightarrow 75%) for the right and the left eye.

Predictor variables:

Preservative is defined as a substance or a chemical that is added to pharmaceutical drugs and other products to prevent decomposition by microbial growth or by undesirable chemical changes. Operationally, a preservative is defined as any of the following substances in the specification of the prescribed eye drops during the period of three months before inclusion into the study: Benzalkonium chloride, Polyquaternium-1, and Boric acid. The preservative is registered on a dichotomous scale where preservative=1 and no preservative=0.

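### The preservative predictor is a closed three-agent list registered only as yes/no, so a drop with an unlisted preservative counts as unpreserved and no result can be attributed to benzalkonium chloride

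*Protocol*

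**What the plan says.** The Predictor variables section of the Protocol first describes a preservative in general terms, as a substance put into a product to stop it decomposing through microbial growth or chemical change. It then gives an operational definition: any of three substances in the product specification over the three months before inclusion. List and code read "Benzalkonium chloride, Polyquaternium-1, and Boric acid. The preservative is registered on a dichotomous scale where preservative=1 and no preservative=0".

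The Introduction explains the interest in preservatives mainly through one agent: "Ocular surface toxicity, especially to benzalkonium chloride (BAK) preservative, has been established and thoroughly discussed in the literature".

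Research question 2 asks whether signs and symptoms are "related to added preservatives in the IOP-lowering eye drops". Main hypotheses 1 and 2 state that the frequency of signs, and of symptoms, "is greater in patients that are on eye drops with preservatives compared with those that are not". The same variable is an adjustment factor in secondary hypotheses 3 and 4.

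On the source of the data, the Measurements section says that "the preservatives in the topical IOP-lowering medication will be collected from the patient journals". The planned sample is 30 subjects (60 eyes), set by feasibility.

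**The concern.** There are two separate weaknesses in how the variable is captured.

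- **Closed list.** The operational definition does not cover everything the conceptual definition covers. Read literally, a patient on a drop preserved with a fourth agent is coded 0. That puts a preserved patient into the unpreserved comparator, which affects hypotheses 1 and 2 exactly as worded.
- **Agent discarded.** The active substance is registered on a four-level nominal scale, but the preservative gets a single yes/no. If the coded-1 group mixes agents, the data set cannot show whether BAK or preservation in general is associated with ocular surface disease. The stated aim of helping to individualise treatment depends partly on that distinction.

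This is a definition of what is recorded. An analysis plan can choose contrasts, but it cannot split a variable by an agent that was not recorded.

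**Working it through.** **Comparing the passages.** The conceptual definition is open (any preserving substance). The operational one is closed (three agents). Code 0 is labelled no preservative, yet under the operational rule it means none of these three. The two coincide only if no patient uses an unlisted agent, and the Protocol does not say so.

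**Size.** The Protocol gives no power calculation, expected difference, agent mix or rate by agent, so there is no figure to reproduce. The following is illustration on assumed inputs:

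- rate of ocular surface disease 40% with no preservative and 70% on BAK, so d = 30 points (assumed);
- s = share of coded-1 patients on BAK (assumed 1, 0.75 or 0.5);
- m = share of coded-0 patients on an unlisted preservative (assumed 0 or 0.2);
- f = effect of non-BAK agents as a fraction of the BAK effect, from 0 (harmless) to 1 (as harmful as BAK), the same for listed and unlisted agents.

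Coded-1 rate = 40 + d[s + (1 − s)f]. Coded-0 rate = 40 + d·m·f. Observed difference = d[s + (1 − s)f − m·f].

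| s | m | f = 0 | f = 0.5 | f = 1 |
|---|---|---|---|---|
| 1 | 0 | 30 | 30 | 30 |
| 0.75 | 0 | 22.5 | 26.25 | 30 |
| 0.5 | 0 | 15 | 22.5 | 30 |
| 1 | 0.2 | 30 | 27 | 24 |
| 0.75 | 0.2 | 22.5 | 23.25 | 24 |
| 0.5 | 0.2 | 15 | 19.5 | 24 |

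For example, s = 0.5, m = 0.2, f = 0.5 gives 30 × (0.5 + 0.25 − 0.1) = 19.5.

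The shortfall from 30 splits into two parts. Pooling costs d(1 − s)(1 − f), which is 7.5(1 − f) points at s = 0.75 and 15(1 − f) at s = 0.5. The closed list costs d·m·f = 30 × 0.2 × f = 6f points. The first vanishes at f = 1 and the second at f = 0, so they trade off against each other.

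**Which contrast is stronger at 30 subjects.** Assume 15 preserved and 15 unpreserved subjects, one outcome per subject, two-sided 5%, and m = 0. BAK-only drops the non-BAK users.

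| Assumed rates, none vs BAK | s | Pooled, f = 0 | Pooled, f = 1 | BAK-only |
|---|---|---|---|---|
| 22% vs 78% | 0.75 | 66% | 91% | 86% |
| 22% vs 78% | 0.5 | 35% | 91% | 76% |
| 30% vs 60% | 0.75 | 23% | 37% | 33% |
| 30% vs 60% | 0.5 | 13% | 37% | 27% |

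The 22% and 78% are the ends of the overall prevalence range in the Introduction. They are not rates by preservative and serve only as bounds. Neither contrast wins throughout: pooling is better when other agents are as harmful as BAK, and worse when they are harmless.

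**The case against.** The strongest reply is that the code fits the question asked. Research question 2 and hypotheses 1 and 2 concern preservatives in general, and none names BAK. The Introduction says especially BAK, not only BAK, and the practical choice it raises is preserved against preservative-free drops. This stands. A reader might infer that hypotheses 1 and 2 test the wrong contrast, or that dilution is established. The Protocol supports neither: dilution needs a material share of non-BAK users and a weaker effect of their agents, and it states neither.

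A second reply is that the loss can be repaired. Preservatives are read from the journals, and the key linking names to IDs is kept for five years after completion, so the agent could be looked up again for 30 patients. The data registration form (Appendix 4) is not shown and may hold more than the Protocol says. This also stands. A reader might call the loss irreversible, but only the registered variable as defined lacks the agent. The Protocol does not, however, plan to go back for it.

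A third reply is that nothing shows any patient at this clinic uses an unlisted preservative. That is true, and it limits the claim to what the rule would do. It does not remove the mismatch between the two definitions.

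**Conclusion.** The point holds as a defect of definition and data capture. By the Protocol's own rule, a drop preserved with an unlisted agent is coded as unpreserved. Whenever agents are mixed in the coded-1 group, neither an association nor a null result can be attributed to BAK. That loss of attribution needs no assumption about effect sizes.

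Attenuation is conditional and its size unknown. On the assumed 30-point effect with 20% of the comparator misclassified and one common non-BAK effect, the observed difference is 22.5 to 24 points (a quarter non-BAK) or 15 to 24 points (half). A reader might combine the worst case of each mechanism: 62.5 − 46 = 16.5 and 55 − 46 = 9 points. Those figures require listed non-BAK agents to be harmless while unlisted ones are as harmful as BAK, and nothing in the Protocol supports that pairing.

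The any-versus-none contrast itself is not wrong. The change is worth making because it is cheap and widens what the study can conclude.

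**What to change.** In the Predictor variables section and the data registration form, register the named preservative from the product specification: 0 = no preservative of any kind, 1 = BAK, 2 = other preservative, named. This brings the operational definition into line with the conceptual one.

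Keep any preservative versus none (codes 1 and 2 against 0) as the contrast for hypotheses 1 and 2 and as the adjustment term in secondary hypotheses 3 and 4. Prespecify BAK versus none as a supporting comparison, and report the other-preservative group descriptively with its agents listed.

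The cost is one extra coded field for 30 patients, from a source already being read. The downside is that the supporting contrast will be sparse and should be read as an estimate with its interval. Restating hypotheses 1 and 2 as BAK versus none is not recommended: it would change the research question and drop patients from a small study, with no assurance of more power.
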